## **Male Participants**

- 4. If male, agrees to the following during the intervention period and for at least 7 days after the last dose of MK-1088:
- Abstains from heterosexual intercourse as their preferred and usual lifestyle (abstinent on a long-term and persistent basis) and agrees to remain abstinent

OR

- Uses contraception unless confirmed to be azoospermic (vasectomized or secondary to medical cause, documented from the site personnel's review of the participant's medical records, medical examination, or medical history interview) as detailed below:
  - Uses a male condom plus partner use of an additional contraceptive method when having penile-vaginal intercourse with a WOCBP who is not currently pregnant.
     Note: Men with a pregnant or breastfeeding partner must agree to remain abstinent from penile-vaginal intercourse or use a male condom during each episode of penilevaginal penetration.

- Contraceptive use by men should be consistent with local regulations regarding the methods of contraception for those participating in clinical studies.

## Female Participants

- 5. A female participant is eligible to participate if she is not pregnant or breastfeeding, and at least one of the following conditions applies:
- Not a WOCBP

OR

- A WOCBP and:
  - Uses a contraceptive method that is highly effective (with a failure rate of <1% per year), with low user dependency, or be abstinent from heterosexual intercourse as their preferred and usual lifestyle (abstinent on a long-term and persistent basis), as described in Appendix 5 during the intervention period and for at least 7 days after the last dose of MK-1088 and for at least 120 days after the last dose of pembrolizumab, whichever occurs last after the last dose of study intervention. The investigator should evaluate the potential for contraceptive method failure (ie, noncompliance, recently initiated) in relationship to the first dose of study intervention. Contraceptive use by women should be consistent with local regulations regarding the methods of contraception for those participating in clinical studies.
  - Has a negative highly sensitive pregnancy test ([urine or serum] as required by local regulations) within 24 hours before the first dose of study intervention. If a urine test cannot be confirmed as negative (eg, an ambiguous result), a serum pregnancy test is required. In such cases, the participant must be excluded from participation if the serum pregnancy result is positive. Additional requirements for pregnancy testing during and after study intervention are in Section 8.3.5.
  - Abstains from breastfeeding during the study intervention period and for at least 7 days after study intervention with MK-1088 or 120 days from the last dose of pembrolizumab.
  - Medical history, menstrual history, and recent sexual activity has been reviewed by the investigator to decrease the risk for inclusion of a woman with an early undetected pregnancy.

#### **Informed Consent**

6. The participant (or legally acceptable representative) has provided documented informed consent/assent for the study. The participant may also provide consent/assent for FBR. However, the participant may participate in the study without participating in FBR.

## **Additional Categories**

7. Archival tumor tissue sample or newly obtained core needle biopsy of a tumor lesion not previously irradiated has been provided. Details pertaining to tumor tissue submission can be found in the Procedures or Laboratory Manual.

8. Adequate organ function as defined in Table 4. Specimens must be collected within 72 hours before the start of study intervention.

Table 4 Adequate Organ Function Laboratory Values

System	Laboratory Value		
Hematological			
Absolute neutrophil count (ANC)	≥1500/µL		
Platelets	≥100 000/µL		
Hemoglobin	≥9.0 g/dL or ≥5.6 mmol/L a		
Renal			
Measured or calculated b creatinine clearance	≥30 mL/min		
Hepatic			
Total bilirubin	≤1.5 ×ULN OR direct bilirubin ≤ULN for participants with total bilirubin levels >1.5 × ULN		
AST (SGOT) and ALT (SGPT)	≤2.5 × ULN (≤5 × ULN for participants with liver metastases)		
Coagulation			
International normalized ratio (INR) OR prothrombin time (PT) Activated partial thromboplastin time (aPTT)	≤1.5 × ULN unless participant is receiving anticoagulant therapy as long as PT or PTT is within therapeutic range of intended use of anticoagulants		

ALT (SGPT)=alanine aminotransferase (serum glutamic pyruvic transaminase); AST (SGOT)=aspartate aminotransferase (serum glutamic oxaloacetic transaminase); GFR=glomerular filtration rate; ULN=upper limit of normal.

- a Criteria must be met without erythropoietin dependency and without packed red blood cell (pRBC) transfusion within last 2 weeks.
- b Creatinine clearance (CrCl) must be calculated using Cockcroft Gault formula.

  Note: This table includes eligibility defining laboratory value requirements for treatments.

Note: This table includes eligibility-defining laboratory value requirements for treatment; laboratory value requirements should be adapted according to local regulations and guidelines for the administration of specific chemotherapies.

- 9. Have an ECOG Performance Status of 0 to 1 assessed within 72 hours before the first dose of study intervention.
- 10. HIV-infected participants must have well controlled HIV on ART, defined as:
  - a. Participants on ART must have a CD4+ T-cell count >350 cells/mm³ at the time of screening.

- b. Participants on ART must have achieved and maintained virologic suppression defined as confirmed HIV RNA level below 50 or the LLOQ (below the limit of detection) using the locally available assay at the time of screening and for at least 12 weeks before screening.
- c. Participants on ART must have been on a stable regimen, without changes in drugs or dose modification, for at least 4 weeks before study entry (Day 1).
- d. The combination ART regimen must not contain any antiretroviral medications other than: abacavir, dolutegravir, emtricitabine, lamivudine, raltegravir, rilpivirine, or tenoforvir.
- 11. Participants who are HBsAg positive are eligible if they have received HBV antiviral therapy for at least 4 weeks and have undetectable HBV viral load before treatment allocation.

Note: Participants should remain on antiviral therapy throughout study intervention and follow local guidelines for HBV antiviral therapy post completion of study intervention.

Hepatitis B screening tests are not required unless:

- Known history of HBV infection
- As mandated by local health authority
- 12. Participants with history of HCV infection are eligible if HCV viral load is undetectable at screening.

Note: Participants must have completed curative antiviral therapy at least 4 weeks before treatment allocation.

Hepatitis C screening tests are not required unless:

- Known history of HCV infection
- As mandated by local health authority
- 13. Be able to swallow and retain oral medication and must not have any clinically significant gastrointestinal abnormalities that may alter absorption.

#### 5.2 Exclusion Criteria

The participant must be excluded from the study if the participant meets the following criteria:

#### 5.2.1 Exclusion Criteria for Arm 1 and Arm 2

The exclusion criteria apply to all participants unless otherwise indicated.

#### **Medical Conditions**

- 1. Has had chemotherapy, definitive radiation, or biological cancer therapy within 4 weeks (2 weeks for palliative radiation) before the first dose of study intervention, or has not recovered to CTCAE Grade 1 or better from any AEs that were due to cancer therapeutics administered more than 4 weeks earlier (this includes participants with previous immunomodulatory therapy with residual immune-related AEs). Participants receiving ongoing replacement hormone therapy for endocrine immune-related AEs will not be excluded from participation in this study.
- 2. Has a history of a second malignancy, unless potentially curative treatment has been completed with no evidence of malignancy for 2 years.
  - Note: The time requirement does not apply to participants who underwent successful definitive resection of basal cell carcinoma of the skin, squamous cell carcinoma of the skin, in situ cervical cancer, or other in situ cancers.
- 3. Has clinically active CNS metastases and/or carcinomatous meningitis. Participants with previously treated brain or meningeal metastases may participate and be eligible for treatment provided they are stable and asymptomatic (without evidence of progression by MRI scan of the brain separated by at least 4 weeks after treatment), have no evidence of new or enlarging brain metastases, are evaluated within 4 weeks before first study intervention administration, and are off immunosuppressive doses of systemic steroids at least 2 weeks before enrollment.
- 4. Has had a severe hypersensitivity reaction to treatment with a monoclonal antibody/components of the study intervention.
- 5. Has an active infection requiring therapy.
- 6. Has a history of interstitial lung disease.
- 7. Has a history of (noninfectious) pneumonitis that required steroids or current pneumonitis.
- 8. Has an active autoimmune disease that has required systemic treatment in the past 2 years (ie, with use of disease modifying agents, corticosteroids, or immunosuppressive drugs) except vitiligo or resolved childhood asthma/atopy. Replacement therapy, such as thyroxine, insulin, or physiologic corticosteroid replacement therapy for adrenal or pituitary insufficiency, is not considered a form of systemic treatment and is allowed. Use of nonsystemic steroids is permitted.

 Has concurrent active Hepatitis B (defined as HBsAg positive and/or detectable HBV DNA) and Hepatitis C virus (defined as anti-HCV Ab positive and detectable HCV RNA) infection.

Note: Hepatitis B and C screening tests are not required unless:

- Known history of HBV and HCV infection
- As mandated by local health authority
- 10. HIV-infected participants with a history of Kaposi's sarcoma and/or Multicentric Castleman's Disease.
- 11. Has a history or current evidence of any condition, therapy, laboratory abnormality, or other circumstance that might confound the results of the study or interfere with the participant's participation for the full duration of the study, such that it is not in the best interest of the participant to participate, in the opinion of the treating investigator.
- 12. Has known psychiatric or substance abuse disorders that would interfere with the participant's ability to cooperate with the requirements of the study.
- 13. Is pregnant or breastfeeding, or expecting to conceive or father children within the projected duration of the study, starting with the screening visit through the duration of contraception after the last dose of study intervention.
- 14. Has not fully recovered from any effects of major surgery without significant detectable infection. Surgeries that required general anesthesia must be completed at least 2 weeks before first study intervention administration. Surgery requiring regional/epidural anesthesia must be completed at least 72 hours before first study intervention administration and participants should be recovered.
- 15. Has a history or current evidence of a GI condition (eg, inflammatory bowel disease, Crohn's disease, ulcerative colitis) or impaired liver function or diseases that in the opinion of the investigator may significantly alter the absorption or metabolism of oral medications; any condition, therapy, or laboratory abnormality that might confound the results of the study, interfere with the participant's participation for the full duration of the study, make administration of the study drugs hazardous, or make it difficult to monitor adverse effects such that it is not in the best interest of the participant to participate, in the opinion of the treating investigator.
- 16. Has clinically significant cardiovascular disease within 12 months from first dose of study intervention, including NYHA Class III or IV congestive heart failure, unstable angina, myocardial infarction, cerebral vascular accident, or cardiac arrhythmia associated with hemodynamic instability. Note: Medically controlled arrhythmia would be permitted.
- 17. Has a QTcF >470 msec.

52

18. History of an allogeneic stem cell transplant or a solid organ transplant.

## **Prior/Concomitant Therapy**

- 19. Has received prior therapy with an anti-PD-1, anti-PD-L1, or anti-PD-L2 agent or with an agent directed to another stimulatory or coinhibitory T-cell receptor (eg, CTLA-4, OX-40, CD137), AND was discontinued from that treatment due to a Grade 3 or higher irAE.
- 20. Has received prior  $A_{2A}$  or  $A_{2B}$  receptor antagonist therapy.
- 21. Currently receiving strong/moderate CYP3A4 inducers or inhibitors.
- 22. Currently receiving H2 blockers or proton-pump inhibitors.
- 23. Has received prior systemic anticancer therapy including investigational agents within 4 weeks before allocation.

Note: Participants must have recovered from all AEs due to previous therapies to ≤Grade 1 or baseline. Participants with ≤Grade 2 neuropathy may be eligible. Participants with endocrine-related AEs Grade ≤2 requiring treatment or hormone replacement may be eligible.

24. Has received prior radiotherapy within 2 weeks of start of study intervention, or had radiation-related toxicities requiring corticosteroids.

Note: Two or fewer weeks of palliative radiotherapy for non-CNS disease, with a 1-week washout, is permitted.

25. Has received a live or live-attenuated vaccine within 30 days before the first dose of study intervention. Administration of killed vaccines are allowed.

Refer to Section 6.5 for information on COVID-19 vaccines.

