## 5.3 Lifestyle Considerations

## 5.3.1 Meals and Dietary Restrictions

Participants are required to fast 2 hours predose and 1 hour postdose.

Foods that are CYP3A inhibitors must not be consumed during the study. Grapefruit and star fruit are known to be CYP3A inhibitors, and should not be consumed for 2 weeks before the first dose of MK-1088 and for the entire duration of the study. Consumption of CYP3A4 inhibitors, such as grapefruit juice, may significantly increase the levels of MK-1088 and cause increased toxicity. St. John's Wort is a CYP3A inducer, and the consumption of St. John's Wort or products containing St. John's Wort may reduce the levels of MK-1088. A partial list of examples of CYP3A inhibitors is provided in Section 6.5.

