## H2 Blockers or PPI

The participant must not take H2 blockers or PPI during the trial from 5 days before the start of the study treatment to 5 days after the last administration of MK-1088. The investigator should use their medical judgment when a participant presents with an H2 blocker or PPI treatment or call the Sponsor Clinical Director for clarification.

Of note, antacids, such as calcium carbonate or aluminum hydroxide-based product, will be allowed during the study, and are recommended to be taken either 4 hours before or after dosing of MK-1088.

• Strong/moderate inhibitors/inducers/substrates of the CYP3A4 enzymes.

Investigators should check an actively updated list of drugs that are clinically relevant substrates, inducers or inhibitors of cytochrome P450, including CYP3A4 (http://medicine.iupui.edu/clinpharm/ddis/table.asp) as well as the product labeling of these compounds for reference.

CYP3A4 inhibitors/inducers/substrates are listed below. The participant must not take the treatments listed in Table 6 during the trial after the start of the study treatment. Since this list is not comprehensive, the investigator should use their medical judgment when a participant presents with a medication not on the list or call the Sponsor Clinical Director for clarification.

Table 6 Examples of Medications, Supplements, and Other Substances Prohibited During the Trial

Strong 3A4	Strong CYP3A4	Moderate CYP3A4	CYP3A4 Substrates With Narrow
Inducers a,d	Inhibitors b,d	Inhibitors b,d	Therapeutic Range c,d
carbamazepine phenobarbital phenytoin rifabutin rifampin troglitazone	indinavir nelfinavir ritonavir clarithromycin itraconazole ketoconazole nefazodone atazanavir saquinavir telithromycin	amprenavir aprepitant diltiazem erythromycin fluconazole fosamprenavir verapamil grapefruit juice	alfentanil c ergotamine c diergotamine c cyclosporine c fentanyl c pimozide c quinidine c sirolimus c tacrolimus c astemizole c,e terfenadine c,e cisapride c,e paclitaxel c repaglinide c lurasidone c

Strong 3A4	Strong CYP3A4	Moderate CYP3A4	CYP3A4 Substrates With Narrow
Inducers a,d	Inhibitors b,d	Inhibitors b,d	Therapeutic Range c,d

Abbreviation: CYP = cytochrome P450.

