- a Strong 3A4 inducers listed are those that decrease plasma AUC values of 3A4 substrates by 30% or higher.
- b Moderate inhibitors are defined as causing a ≥2- but <5-fold increase in the AUC values or 50-80% decrease in clearance of sensitive CYP3A substrates when the inhibitors were given at the highest approved dose and the shortest dosing interval in clinical evaluations. Strong inhibitors are defined as causing a ≥5-fold increase in the plasma AUC values or more than 80% decrease in clearance.
- CYP3A4 substrates with narrow therapeutic range refers to drugs whose exposure-response indicates that increases in their exposure levels by the concomitant use of CYP3A4 inhibitors may lead to serious safety concerns. For specific information, see the Classification of Substrates tables available at:
  - http://www.fda.gov/Drugs/DevelopmentApprovalProcess/DevelopmentResources/DrugInteractionsLabeling/ (then click "Drug Development and Drug Interactions: Table of Substrates, Inhibitors and Inducers")
- d Compiled from the in vivo inhibitors and inducers, inhibitor classification, and substrate classification tables available at:
  - http://www.fda.gov/Drugs/DevelopmentApprovalProcess/DevelopmentResources/DrugInteractionsLabeling/ (then click "Drug Development and Drug Interactions: Table of Substrates, Inhibitors and Inducers") and from the CYP450 drug interaction table (accessed June 2012) available at: http://medicine.iupui.edu/clinpharm/DDIs/table.aspx
- e Not available in the United States, and limited availability in the European Union.

If the investigator determines that a participant requires any of the aforementioned treatments for any reason, study intervention must be discontinued.

All treatments that the investigator considers necessary for a participant's welfare may be administered at the discretion of the investigator in keeping with the community standards of medical care. All concomitant medication will be recorded on the eCRF including all prescription, over-the-counter products, herbal supplements, and IV medications and fluids. If changes occur during the study period, documentation of drug dosage, frequency, route and date should also be included on the eCRF.

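### No drug-free interval before first dose is required for 16 of the 24 CYP3A4 inhibitors and inducers given as examples in Table 6, although grapefruit has 2 weeks

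*Combined protocol and SAP*

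**What the plan says.** Criterion 21 (section 5.2.1) excludes those "Currently receiving strong/moderate CYP3A4 inducers or inhibitors" and gives no number of days. Section 6.5 then says "The participant must not take the treatments listed in Table 6 during the trial after the start of the study treatment", and closes by restricting prohibited medications during the treatment phase.

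Section 5.3.1 treats grapefruit and star fruit differently: they "should not be consumed for 2 weeks before the first dose of MK-1088 and for the entire duration of the study". It warns that CYP3A4 inhibitors "may significantly increase the levels of MK-1088 and cause increased toxicity". Grapefruit juice is itself in Table 6, in the moderate inhibitor column: "amprenavir aprepitant diltiazem erythromycin fluconazole fosamprenavir verapamil grapefruit juice".

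For HIV-infected participants, inclusion criterion 10c requires that those on antiretroviral therapy "must have been on a stable regimen, without changes in drugs or dose modification, for at least 4 weeks before study entry", and criterion 10d limits the regimen to a list that contains no protease inhibitor. Once treatment has begun, section 6.5 is strict: "If the investigator determines that a participant requires any of the aforementioned treatments for any reason, study intervention must be discontinued".

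**The concern.** Inhibition or induction can outlast the last dose of the interacting drug. The plan accepts this for grapefruit, where it asks for 2 weeks, but sets no interval for ketoconazole, itraconazole or clarithromycin, which the same table classes as strong inhibitors, or for any listed inducer.

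The period at risk is the one that drives dose-finding. Full PK sampling starts on Cycle 1 Day 1, and the DLT window is Cycle 1 (section 6.6.2). Dose reductions are not allowed in that cycle (section 6.6.4). A qualifying toxicity judged at least possibly related to study intervention counts in Table 3, and residual inhibition is not among the reasons in section 5.5 for treating a participant as non-evaluable. Section 4.3.1.3 allows PK and safety data to adjust the escalation schedule, but this is optional and does not remove a DLT from the count.

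At stake are avoidable over-exposure in the first study of MK-1088 in patients, distorted first-dose PK, and a DLT count that may partly reflect another drug. Residual induction could work the other way and lower exposure.

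**Working it through.** **Coverage count (inhibitor and inducer columns of Table 6)**

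- Strong inducers 6, strong inhibitors 10, moderate inhibitors 8: 6 + 10 + 8 = 24.
- Covered by criteria 10c and 10d when used as antiretroviral therapy: indinavir, nelfinavir, ritonavir, atazanavir, saquinavir, amprenavir, fosamprenavir = 7, in effect 4 weeks.
- Covered by section 5.3.1: grapefruit juice = 1, 2 weeks.
- Not covered: 24 − 7 − 1 = 16.

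The 16 are five strong inhibitors (clarithromycin, itraconazole, ketoconazole, nefazodone, telithromycin), five moderate inhibitors (aprepitant, diltiazem, erythromycin, fluconazole, verapamil) and all six inducers (carbamazepine, phenobarbital, phenytoin, rifabutin, rifampin, troglitazone).

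**Whether another rule supplies the interval**

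- Criteria 11 and 15 leave confounding therapy to the investigator's opinion.
- Criterion 5 excludes active infection requiring therapy, but sets nothing after an azole or macrolide course ends.
- Section 6.5 opens by disallowing excluded drugs during the ongoing study. Even if that starts at consent, screening runs from Day −28 to Day −1, so no minimum drug-free time follows.
- Section 8.1.5.1 has the investigator check any washout the protocol specifies, but none is specified for these drugs.

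**Scale of exposure**

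Table 6 footnote b says "Moderate inhibitors are defined as causing a ≥2- but <5-fold increase in the AUC values" for sensitive substrates, and at least 5-fold for strong inhibitors. The planned dose steps are 200/100 = 2, 400/200 = 2, 600/400 = 1.5 and 800/600 = 1.33. The class definitions therefore match or exceed a full dose step. They describe full inhibition of a sensitive substrate. The documents do not say how sensitive MK-1088 is, and the effect of a stopped drug would be smaller and falling. The possible range starts at no effect.

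**DLT illustration (assumptions only)**

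Assume a cohort of 3, two participants with DLT risk 0.10, one affected participant with risk q, and three unaffected participants (risk 0.10) added after 1 DLT in 3. Table 3 gives 0/3 = E, 1/3 = S, 2/3 = D, 3/3 = DU and 1/6 = E. The cap of three added participants after 1/3 is in section 4.3.1.3.

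- P(0/3) = 0.9² × (1 − q) = 0.81(1 − q)
- P(1/3) = 2 × 0.1 × 0.9 × (1 − q) + 0.81q = 0.18(1 − q) + 0.81q
- P(no DLT in the three added) = 0.9³ = 0.729
- P(not escalated by 6) = 1 − P(0/3) − 0.729 × P(1/3)

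| q | P(0/3) | P(1/3) | Not escalated at 3 | Not escalated by 6 |
|---|---|---|---|---|
| 0.10 (no effect) | 0.7290 | 0.2430 | 0.2710 | 0.0939 |
| 0.15 | 0.6885 | 0.2745 | 0.3115 | 0.1114 |
| 0.40 | 0.4860 | 0.4320 | 0.5140 | 0.1991 |

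By six participants the chance of not having escalated goes from 9.4% to between 11.1% and 19.9%.

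**The case against.** The case against has several parts, and much of it stands.

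- **Size.** A reader might infer from the three-participant column that one such enrolment could take the chance of not escalating from 27% to 51%. That treats a Stay after 1/3 as final. Table 3 allows escalation at 1/6, so much of the difference is delay. The values of q have no source in the documents and hold the raised risk for all 21 days, although the effect would fade.
- **The 2-week figure.** Section 5.3.1 explains why inhibitors should be avoided, not why the interval is 2 weeks. It does not support reading 2 weeks as a sufficient washout for every drug in Table 6.
- **Frequency.** A reader might infer that participants with controlled arrhythmia or treated brain metastases will often have just come off verapamil or an anticonvulsant. Criteria 3 and 16 admit such participants but mention neither drug class, so this is speculation.
- **Safeguards.** Anyone found taking a listed drug when eligibility is checked fails criterion 21, and rescreening needs sponsor consultation with written documentation (section 5.4). Criterion 11 also covers past therapy. These make the case less likely, but they supply no minimum interval.
- **The denominator.** Table 6 is a list of examples, so 16 of 24 describes the listed drugs and does not measure coverage of the class.
- **On-study rule.** Requiring discontinuation when a listed drug is needed concerns ongoing co-administration. It does not contradict a lighter rule for past use.

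None of this identifies a required interval for the 16 drugs.

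**Conclusion.** The gap is real. As written, the rules admit a participant who stopped itraconazole or rifampin the day before Cycle 1 Day 1, unless the investigator uses discretion, while asking for 2 weeks off grapefruit. Residual inhibition or induction could then reach Day 1 PK, Cycle 1 safety and the DLT count.

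The coverage count rests on the text alone. The consequence cannot be sized: MK-1088's sensitivity to CYP3A4, the offset time of each drug and the number of affected participants are not given. The illustrated rise of 1.8 to 10.5 percentage points (11.1 − 9.4 and 19.9 − 9.4, from unrounded values) depends wholly on the assumed risks. It is conditional on an affected participant being in the cohort.

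The documents do not support the stronger reading that dose-finding is materially biased or that the trial is likely to select the wrong dose. This is a cheap improvement to an eligibility rule. The mismatch between criterion 22 (current use of acid reducers) and the 5-day window in section 6.5 is editorial, because section 6.5 already binds every participant.

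**What to change.** In criterion 21, and in the section 6.5 sentence that introduces Table 6, require a minimum drug-free interval before first dose for strong and moderate CYP3A4 inhibitors and inducers. Set it at no less than 2 weeks, in line with the grapefruit rule, and longer for individual drugs where the sponsor's pharmacology data require it. The sponsor should confirm the length, since the documents do not justify 2 weeks drug by drug. Leave the column of narrow-therapeutic-range substrates unchanged, because the concern there is the effect on the other drug. Optionally, copy the 5-day H2 blocker and PPI window into criterion 22 for consistency.

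The cost is wording in criterion 21 and one sentence of section 6.5. No new data are needed: prior medication is already recorded for 28 days (section 8.1.5.1), and 14 days fits inside the 28-day screening window. The downside is that a few participants wait slightly longer or are not eligible, including any who cannot safely come off a listed drug for that long.
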